#### **4.1 Accrual goal**

The accrual goal for this study is 230 patients or approximately 46 patients per year for 5 years.

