#### 10.2.3 Area under ROC curves as predictive measure and incremental prediction improvement for progression

Patients will be categorized at baseline by NCCN risk class ranging from very low risk to intermediate risk and into those who progressed while on the trial and those who did not. Logistic regression will be used to model the association between NCCN risk class and progression using AUC for ROC curves. The incremental benefit of mpMRI, genomic testing and molecular markers compared to NCCN risk alone will be evaluated by comparing AUC using a likelihood ratio test. MRI will be categorized from 1-5 using PIRADS, while genomic test scores and molecular markers can be used as continuous scores or categorized into levels of risk (low/ intermediate/high).

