### **10.4 Sample size, accrual rate and study duration**

We plan to accrue approximately 55 patients per year for the first three years of the study; this assumes a 10% dropout rate. The power (97.3%), is based on 150 patients, using a two-sided binomial test at the 5% significance level to detect an increase in the 24-month cumulative progression rate from 12.5%, as expected for AS historically, to 25% for MRI-AS. Enrollment will occur during the first 3.25 years. Enrollment will be completed at < 3.33 years from the enrollment of the last patient.

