receiver's operating characteristic curve (AUC) with 10-fold cross-validation approach to evaluate performance of prediction model. Radiomic profiles on multi-parametric MRI that suggest regions of the prostate that are suspicious for more aggressive prostate cancer will be correlated to histopathologic findings from biopsy of these regions. Genomic profiles from tissue cores in each region will be correlated to radiomic profiles and histopathology from that region to see what each adds to improving the ability to predict patients who are likely to harbor more aggressive tumors that would portend poor outcome on active surveillance. Radiomic and genomic profiles from MRI targeted biopsies will be compared to segmental biopsies to see if profiles from targeted biopsies are more informative for risk assessment compared to segmental biopsy using longitudinal analysis approach. We will also assess how these profiles change over time in serial imaging and biopsy and see if/ how these profile changes correlate to change in histopathology. We will also relate genomic and radiomic profiles of the prostate to common serum and urinary markers that have been used predict progression on active surveillance. For continuous outcomes, association between outcome and other covariates will be examined using linear regression model and correlation coefficient. For binary outcomes and time-to-event outcomes, logistic regression and Cox proportional hazards regression will be used, respectively. All tests will be two-sided and statistical significance will be considered when  $p < .05$  after multiplicity adjustment.

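### Added value over NCCN class is to be judged by comparing AUCs with a likelihood ratio test, which gives no estimate or interval for the AUC gain, and no optimism correction is assigned to that gain

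*Combined protocol and SAP*

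**What the plan says.** Section 10.2.3 serves secondary objective 3 in Section 3.2. Men are grouped at baseline by "NCCN risk class ranging from very low risk to intermediate risk", and logistic regression relates class to progression on the trial. The gain from mpMRI, genomic testing and molecular markers is then "evaluated by comparing AUC using a likelihood ratio test". Section 10.3.3 repeats this method for progression on the baseline biopsy, as an exploratory endpoint.

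On predictor form, Section 10.2.3 says "MRI will be categorized from 1-5 using PIRADS", and that genomic scores and molecular markers "can be used as continuous scores or categorized into levels of risk". It gives neither the number of markers nor whether they enter singly or together. Neither section mentions a confidence interval or internal validation for the AUC gain.

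Section 10.5 plans AUC with a "10-fold cross-validation approach to evaluate performance of prediction model". That sentence directly follows the description of the radiomic and gene-signature classifier and does not refer to 10.2.3 or 10.3.3.

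**The concern.** The plan names one quantity as the measure of benefit (AUC) and a procedure that addresses another (the difference in log-likelihood between nested models). A likelihood ratio test yields a p-value for whether the added coefficients are all zero. It says nothing about how large the AUC gain is or how precisely it is known.

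The AUC gain is what clinicians will read, and it is the part left unprotected. When a model is enlarged and both AUCs are taken on the data used for fitting, the larger model tends to show the higher AUC even if the new predictors carry no information. A valid p-value could then stand beside an inflated gain and be read as the significance of that gain. Section 1.4.4 lists several candidates (genomic panels, a four-kallikrein test, urinary PCA3), so joint models with several df are plausible.

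**Working it through.** **The plan's own figure.** The only power statement concerns the primary endpoint: "The power (97.3%), is based on 150 patients, using a two-sided binomial test at the 5% significance level", for a rise in the "24-month cumulative progression rate from 12.5%, as expected for AS historically, to 25% for MRI-AS". An exact one-sample binomial test with 0.025 per tail and n = 150 rejects at 28 or more, or 10 or fewer, progressions. The actual two-sided level is 0.0346 and the power 0.9734, so 97.3% reproduces. No power or precision is stated for the AUC analysis.

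**Inputs from the documents.**
- n = 150 (Section 10.4) and 230 ("The accrual goal for this study is 230 patients", Section 4.1). With the 10% dropout of Section 10.4, 230 x 0.9 = 207.
- Event rate 25% at 24 months: 150 x 0.25 = 37.5 events, or 230 x 0.25 = 57.5.
- PI-RADS 1-5: 1 df if linear, 4 df if categorical. Genomic or molecular score: 1 df if continuous, 2 df if three-level.

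**Assumptions not in the documents.**
- Three NCCN classes in a 40/35/25% mix, odds ratio per class 1.0, 1.5 or 2.0 (base AUC about 0.54-0.65).
- PI-RADS mix 15/25/25/25/10%.
- 40% events as an upper case for the whole trial.
- Added predictors independent of outcome and class, that is, useless.

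**Quantities.** AUC = P(score of an event > score of a non-event) + 0.5 P(tie). Apparent gain = AUC(NCCN + markers) - AUC(NCCN), both on the fitting data. Likelihood ratio statistic = 2(l1 - l0), referred to chi-square with the added df. There were 500 simulated trials per setting.

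**Mean apparent gain from useless markers, range over settings.**

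| Added df | Example | Mean gain |
|---|---|---|
| 1 | one continuous marker, or linear PI-RADS | 0.011-0.023 |
| 2 | one three-level genomic class | 0.016-0.036 |
| 3 | linear PI-RADS + genomic score + one marker | 0.023-0.053 |
| 4 | categorical PI-RADS | 0.027-0.068 |
| 6-7 | categorical PI-RADS + genomic score + 1-2 markers | 0.037-0.094 |
| 10 | all categorical | 0.054-0.122 |

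At 1 df the gain was zero or negative in about 5-12% of samples. At 4 or more df it was positive in about 99-100%. A separate run at 25% events added categorical PI-RADS, then a three-level genomic class, then four markers (4, 6 and 10 df). It gave 0.055, 0.072 and 0.102 at n = 150, and 0.043, 0.058 and 0.086 at n = 207. In that run one continuous marker gave 0.013-0.019 and a positive gain in 86-90% of samples.

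**Test behaviour with useless markers.** The likelihood ratio test rejected in 3-10% of samples, mostly 4-8%. Part of that spread is simulation error: sqrt(0.05 x 0.95 / 500) = 0.010. DeLong's test on the same refitted nested models rejected in about 0-2% at 1 df, 17-37% at 6-7 df and 49-65% at 10 df.

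**Effect of correction.** Bootstrap-corrected gain = apparent gain - mean over resamples of [gain in the resample - gain of the resample's models in the original data]. This used 20 resamples, 300 simulated trials per row and odds ratio 1.5.

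| n, events | Added df | Apparent | 10-fold CV | Bootstrap-corrected |
|---|---|---|---|---|
| 150, 25% | 1 | 0.0194 | -0.0042 | 0.0024 |
| 150, 25% | 4 | 0.0493 | -0.0195 | 0.0036 |
| 150, 25% | 7 | 0.0809 | -0.0217 | 0.0115 |
| 230, 25% | 1 | 0.0145 | -0.0047 | 0.0003 |
| 230, 25% | 4 | 0.0388 | -0.0145 | 0.0005 |
| 230, 25% | 7 | 0.0609 | -0.0239 | 0.0045 |
| 207, 40% | 1 | 0.0141 | -0.0039 | 0.0015 |
| 207, 40% | 4 | 0.0355 | -0.0155 | 0.0004 |
| 207, 40% | 7 | 0.0556 | -0.0211 | 0.0014 |

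Both methods remove all or most of the spurious gain. The bootstrap leaves a small residue at 7 df and n = 150. Cross-validation falls slightly below zero, as expected when noise is added to a model and judged on held-out patients.

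**The case against.** The strongest reply is that the likelihood ratio test is the right test here. For correctly specified nested logistic models the two null hypotheses coincide: if the added coefficients are zero, predicted risk and AUC are unchanged; if not, the true risk score has the higher AUC. The simulations agree that it holds its level approximately. This stands in full. A reader might infer from the mismatched wording that the planned p-value is invalid, or that a formal AUC comparison such as DeLong's test should replace it. The first is not so, and the second would be worse at several df.

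Second, the plan never says the AUCs will be computed on the fitting data, and it does mention cross-validation. This also stands: apparent AUCs are an inference from silence, and the plan is not without internal validation. What remains is that the cross-validation is not assigned to these two endpoints.

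Third, the event rate is uncertain. Section 10.2.3 counts progression at any time on the trial, and Section 7.3 follows men to the third annual biopsy, so the rate may exceed the 24-month 25%; more events generally mean less optimism. The 40% case covers this in part. For the baseline-biopsy endpoint of 10.3.3 the plan states no expected rate, and no separate calculation was made.

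**Conclusion.** The point holds in limited form. Sections 10.2.3 and 10.3.3 pair a sound test with a measure it does not estimate, and leave that measure without an interval or an assigned optimism correction. If the AUCs are apparent ones, the average spurious gain is about 0.01-0.02 for one continuous marker and about 0.03-0.12 for joint additions of 4-10 df, under the assumptions listed.

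A reader might take a single inflation figure, such as 0.04-0.10, as a property of this plan. The documents do not support that: such a range fits many joint models of 4-10 df, whereas a single 1-df marker falls below it and sometimes shows no gain at all. The df, coding and mode of entry are all open.

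This concerns one secondary and one exploratory analysis. The primary endpoint and its sample size are unaffected.

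**What to change.** In Sections 10.2.3 and 10.3.3:

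- Name the likelihood ratio test as the test of added value between nested logistic models. Prespecify the markers, their coding (PI-RADS linear or categorical; scores continuous or three-level), single or joint entry, and the resulting df.
- Report the AUC gain separately as an estimate. Correct it for optimism by bootstrap refitting of both models, or by stating that the 10-fold cross-validation of Section 10.5 also covers these models. Give a bootstrap 95% confidence interval for the corrected gain.
- Do not substitute a DeLong test on the refitted nested models.

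The cost is a few lines of code and two edited paragraphs, with no new data, visits or patients. Reported AUC gains will look less favourable.

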#### **3.2 Secondary Objectives**

- 1) To identify whether earlier identification of progression with MRI and MRI-US fusion biopsy will portend improved outcomes of patients undergoing delayed primary surgery or radiation after initial surveillance at the University of Miami
- 2) To determine the effect of multiparametric MRI and MRI-US fusion biopsy on health related quality of life and cancer specific anxiety using patient reported validated questionnaires.
- 3) To determine the incremental benefit of mpMRI, genomic risk test, and molecular marker at baseline compared to NCCN risk class for predicting progression on Active Surveillance

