## 7.5 Prostate Biopsy

Standard antibiotic prophylaxis of will be at the discretion of the physician managing the biopsy. Aspirin, anticoagulants and vitamin supplements will be temporarily discontinued at least one week prior to the procedure, per routine; these drugs may be restarted per standard practice for prostate biopsies (typically a day or two later if there is no bleeding). The typical and recommended procedure involves placement of the patient in the left lateral decubitus position. Immediately prior to the procedure, 10 cc of 1% Lidocaine may be injected into the periprostatic nerve plexus under ultrasound guidance, typically using a 22 gauge 7-inch needle. The syringe is aspirated before the lidocaine injection to prevent unintentional injection into the vascular compartment. An ultrasonographic wheal may be viewed in the sagittal plane between the rectal wall and base of the seminal vesicles.

Transrectal ultrasound biopsies will be performed on an FDA-approved device using standard techniques. Twelve to fourteen needle core biopsies are desired, but the managing physician may opt for fewer, if there are complications or other indications, or more, if an area of interest was felt to be inadequately biopsied (needle misdirection or other reason). The managing physician will be a co-investigator and will understand the protocol goal of 12-14 cores per prostate biopsy. The arrangement that is recommended (not mandatory) will be left lateral base (LLB), left lateral mid (LLM), left lateral apex (LLA), left medial base (LMB), left medial mid (LMM), left medial apex (LMA), right lateral base (RLB), right lateral mid (RLM), right lateral apex (RLA), right medial base (RMB), right medial mid (RMM) and right medial apex (RMA). Transition zone biopsies may be acquired. The MRPlus biopsies will be performed in the same fashion, but corresponding needle cores will be targeted towards the suspicious areas (see Figure 6). During the course of the procedure, hemorrhage may be visualized within the bladder following needle

biopsy. If this is the case, or if gross blood is noted at the urethral meatus, bladder catheterization and clot irrigation may be indicated, as determined by the urologist.

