The procedure will be performed by an urologist in the Department of Urology [name] at the University of Miami. For patients with MRI visible lesions, an MRI-US fusion biopsy will be performed in addition to the standard template (above). MRI-US fusion biopsies will be performed preferably using the Uro-Nav system from Invivo, Philips; although, the Artemis system is available in the department of urology and may be used.

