#### *7.5.1 MRI-Ultrasound (MRI-US) Registration for Targeted Prostate Biopsy*

MRI-US fusion biopsy will be performed on an FDA approved platform (e.g., UroNav, In Vivo). The approach begins with multiparametric MRI of the prostate as described above. Expert radiologists will interpret the MRI with the assistance of in-house and/or commercially available software. Suspicious lesions will be determined based on multiple parameters and delineated on the MRI by a panel of expert radiologists with experience reading prostate MRI. Biopsy needle localization and tracking is recorded by an external magnetic field while the biopsy is performed using freehand transrectal ultrasound. Once the MRI is loaded onto the software platform, an initial transrectal ultrasound sweep of the prostate of the prostate is performed, and a rigid image fusion is performed allowing clinicians to see both the MRI and ultrasound images moving together in real time. The lesion on MRI is then targeted using ultrasound to ensure the correct depth and course of the needle to ensure the needle enters the suspicious area. By using freehand ultrasound, a technique familiar to urologists, the learning curve for the procedure is steep and the workflow preserved allowing a quick procedure for the patient.

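### MRI findings decide who gets extra biopsy cores, and those cores count toward progression, so the incremental AUC of mpMRI over NCCN class can be raised by MRI-dependent sampling

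*Combined protocol and SAP*

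**What the plan says.** Secondary objective 3 (section 3.2) is "To determine the incremental benefit of mpMRI, genomic risk test, and molecular marker at baseline compared to NCCN risk class" as predictors of progression on surveillance. Section 10.2.3 divides men "into those who progressed while on the trial and those who did not", fits logistic regression on NCCN class, and says the added value of each marker "will be evaluated by comparing AUC using a likelihood ratio test". For imaging, "MRI will be categorized from 1-5 using PIRADS". Section 10.3.3 repeats the analysis with progression on the baseline biopsy as the outcome.

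Sampling is described in section 7.5: "For patients with MRI visible lesions, an MRI-US fusion biopsy will be performed in addition to the standard template". Section 7.5.1 says how a target is chosen: "Suspicious lesions will be determined based on multiple parameters and delineated on the MRI by a panel of expert radiologists". Neither section names a PI-RADS cut-off.

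Progression (10.1.1) is met by more than 4 positive cores, three or more cores with 3+4, any core with 4+3 or higher, an upgrade from 3+3 to 3+4, or treatment without histological progression (criterion v). Histological progression (10.1.2) uses the same criteria without treatment. Neither definition separates targeted from template cores or offers a template-only version.

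**The concern.** A man with a visible lesion has the template plus targeted cores; a man without one has the template alone. Every histological criterion becomes easier to meet, or at least no harder, as cores are added. The imaging result is thus used twice: as the predictor, and as the rule that sets how hard the outcome is sought. NCCN class, the comparator, has no stated role in allocating cores.

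Section 10.3.3 is the most exposed, because the baseline MRI directs the very biopsy being predicted. Section 10.2.3 is exposed at the initial biopsy and less directly afterwards. It also has a second possible route: treatment counts as progression, and the plan does not describe keeping the MRI result from the treating physician.

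At stake is the reading of secondary objective 3 and exploratory objective 4. A positive mpMRI result could mean that MRI identifies men whose disease will progress, that men with visible lesions were sampled more, or both. The analysis as planned cannot tell these apart.

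**Working it through.** **The plan's own figures.** The documents give no AUC, AUC difference or power for 10.2.3 or 10.3.3, so there is nothing to reproduce for this analysis. The one stated power (section 10.4: 97.3%, n = 150, 12.5% versus 25%, two-sided 5%) does reproduce: the exact binomial test rejects at 28 or more of 150, with upper-tail error 0.0193 and power 0.9734. It concerns the primary endpoint and is unaffected.

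**Direction, from the text.** (1) A visible lesion leads to fusion cores beyond the template (7.5). (2) All cores feed the progression criteria (10.1.1, 10.1.2). (3) PI-RADS grades the same MRI examination and is the predictor (10.2.3, 10.3.3). (4) Section 10.5 compares targeted with segmental biopsies only for radiomic and genomic profiles, not for the progression outcome used in the mpMRI AUC. (5) Section 1.4.2 itself expects fusion biopsy to show higher grade and volume than traditional biopsy.

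**Size, on assumed inputs.** Let t be the template progression rate, taken as equal in all men (MRI unrelated to template progression); d the points added by targeted cores in men with visible lesions; and s the share with visible lesions. None of the three is in the documents. Then:

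- overall progression P = t + s·d
- sensitivity of the flag = s(t + d)/P
- false-positive rate = s(1 − t − d)/(1 − P)
- AUC = 0.5 + (sensitivity − false-positive rate)/2

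This simplifies to AUC = 0.5 + s(1 − s)d / [2P(1 − P)].

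| t | d | s | P | Sensitivity | False-positive rate | AUC |
|---|---|---|---|---|---|---|
| 0.20 | 0.05 | 0.60 | 0.230 | 0.652 | 0.584 | 0.534 |
| 0.15 | 0.05 | 0.60 | 0.180 | 0.667 | 0.585 | 0.541 |
| 0.20 | 0.10 | 0.40 | 0.240 | 0.500 | 0.368 | 0.566 |
| 0.15 | 0.10 | 0.45 | 0.195 | 0.577 | 0.419 | 0.579 |

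The first and last rows are the extremes over t = 15-20%, d = 5-10 points and s = 40-60%. The range is 0.534 to 0.579, against 0.50 on template cores.

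**A limiting case.** Suppose template progression is 12.5% and targeted cores supply the whole planned rise to 25%. Then s·d = 0.125 and P = 0.25, so AUC = 0.5 + (1 − s)/3. That is 0.70, 0.67, 0.62 and 0.57 for s = 40%, 50%, 65% and 80%.

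**The incremental question.** The flag's stand-alone AUC is not the quantity in 10.2.3, so PI-RADS added to NCCN class was also simulated. The assumptions were template progression 12.5% with an NCCN effect but no MRI effect, PI-RADS 3-5 treated as visible (65% of men), and a targeted-only yield e among men with a visible lesion and no template progression.

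- On template-only progression the AUC gain from MRI is 0.000. On all-core progression it is 0.015, 0.038, 0.083 and 0.093 for e = 5%, 10%, 20% and 22%.
- At n = 150 (600 simulated trials per setting), the 5% likelihood ratio test rejects in about 11%, 18% and 63% of trials for e = 5%, 10% and 22%. On template-only progression it rejects in about 5-7%.

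**The case against.** The strongest counter-argument is that targeted cores find real cancer. Section 1.1 says segmented sampling can miss dominant or high-grade tumours. If MRI points to tumours that the template overlooks, the extra progression is partly true prediction, and an MRI unrelated to template progression is not an MRI without information. This stands: the illustration shows what sampling alone could produce, not what it will produce.

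Dilution also stands for 10.2.3. The predictor is measured at baseline, but MRI is repeated at 12, 24 and 36 months (section 7.2), so later targeting can follow later scans. It does not help 10.3.3.

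The template is not a clean common yardstick. Twelve to fourteen cores are the aim, but fewer or more are allowed and the layout is only recommended (7.5). Sections 1.2 and 4 describe segmented sampling of the rest of the gland, and 7.5 also says that "corresponding needle cores will be targeted towards the suspicious areas", which could mean redirected rather than extra cores. The sentence in 7.5 on men with visible lesions describes addition. These passages are in tension.

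Three stronger readings are tempting, and the documents do not support them:

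- A reader might infer that a PI-RADS score triggers targeting. The stated trigger is a visible or suspicious lesion judged on several parameters; PI-RADS appears only as an analysis category. The link is close, but inferred.
- A reader might call this incorporation bias. PI-RADS is not a component of the progression definition; differential verification is the accurate term.
- A reader might infer that genomic markers are free of the problem and that mpMRI is therefore unfairly favoured over them. Section 1.4.4 takes genomic tissue from MRI-guided biopsies, and 10.2.3 compares markers with NCCN class alone, with no head-to-head between MRI and genomics.

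**Conclusion.** The concern holds as a risk to interpretation, not as a demonstrated bias. The direction follows from the text, provided targeted cores are additional as 7.5 states for men with visible lesions: the same MRI that supplies the predictor also increases sampling, and nothing in 10.2.3 or 10.3.3 separates the two effects. The size cannot be fixed. The stand-alone AUC of about 0.53-0.58 and the simulated gains rest wholly on assumed yields and visible-lesion shares. It would go too far to say that the mpMRI AUC is inflated as a matter of fact, or that all of any observed gain would be artefact.

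Nor do the documents support replacing all-core progression with template-only progression as the main outcome in 10.2.3. Section 7.3 directs men who progress to treatment, although they may decline, so later template results would often be missing, and mostly in men with visible lesions. Coding those men as non-progressors would bias mpMRI downward, while criterion v would bring treated men back in as progressors.

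The point affects secondary objective 3 and exploratory objective 4. The primary endpoint and its power are untouched.

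**What to change.** Before analysis, amend the plan as follows:

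1. Keep all-core progression as the outcome in 10.2.3 and 10.3.3, and state that the resulting mpMRI AUC is conditional on MRI-directed sampling.
2. For 10.3.3, pre-specify the same mpMRI AUC analysis with histological progression scored on template cores only, reported beside the all-core result. This is where it is most informative, since only one biopsy is involved and no follow-up has been lost.
3. For 10.2.3, add the template-core version as a sensitivity analysis. Leave out criterion v, and treat men who go to treatment after targeted-core progression as censored, not as non-progressors. The planned logistic model has no censoring, so this needs a per-biopsy (discrete-time) model or a time-dependent AUC. The censoring may be informative, which is one more reason to keep this as a sensitivity analysis.
4. Record each core as targeted or template. Section 10.5 already presumes that the two can be told apart, but no section states that they are labelled.
5. Reconcile sections 1.2, 4 and 7.5 on whether targeted cores are added to the template or replace part of it. The meaning of a template-only result depends on the answer.

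No new procedure or patient is needed. The cost is fewer events, lower sensitivity for progression in the template-only analyses, and a modest amount of extra data coding and analysis.
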